Investigating Racial Differences in Diet Benefits for Knee Osteoarthritis

Study Protocol & Statistical Analysis Plan

NCT04343716

08/13/2024

[name], Associate Professor, Principal Investigator University of Alabama at Birmingham Birmingham, AL 35294

Study Protocol

A telephone screening interview will be used to assess each participant's OA status and assessment of the reported duration of knee OA, current and past treatments, comorbid conditions, current medication use, dietary conditions and other exclusion criteria. Eligible, participants will be invited to the testing facilities in Campbell Hall for informed consent and baseline measures. Following this visit, participants will record daily food consumption for one week as well as daily pain ratings. After one week, participants will visit the Clinical Research Unit for fasted blood draw and additional testing. Immediately following this session, participants will be asked to select one week of meals and snacks from a menu of commercially-available meals. Study personnel will record the choices and order the meals to be delivered to the participants to initiate the intervention. During the 6-week intervention, participants will be contacted by study personnel weekly to place food orders and be instructed to record any beverages consumed during the week. Every three weeks, participants will return for testing. At the end of 6 weeks, blood will be taken prior to testing/debriefing.

Participants. The investigators will recruit 20 adult women (55-75) with knee OA with equal representation across racial groups (10 AA, 10 NHW). Peak prevalence rates for OA are at the 55-75 years of age, so the investigators feel confident that there will be no trouble recruiting this population. Participants will be recruited using existing databases, community flyers and community outreach. The feasibility trial used prescribed diets and had an attrition rate of 0% in the LCD group. Here, provision of all of the food for the intervention is expected to have lower rates of attrition.

Inclusion criteria will include:

- diagnosis of knee OA;
- pain in at least 4/7 days/week for the past 3 months;
- age between 65-75;
- average daily consumption of >100 g carbohydrates;
- understanding of verbal and written English;
- self-identification as either AA or NHW;
- BMI between 25 and 40 kg/m2.

Exclusion criteria will be the following:

- diabetes:
- unwillingness to follow prescribed diets;
- recent weight change (>4 kg in past month);
- currently on a diet;
- history of eating disorders or other psychiatric disorders;
- digestive diseases;
- difficulty chewing or swallowing;
- reliance on others for meal preparation;
- cardiovascular or pulmonary disease;
- daily opioid pain medications;
- use of medications known to alter metabolism or digestion (e.g., proton-pump inhibitors);
- use of anti-hypertensive medications that affect glucose tolerance;

- use of tobacco;
- participation in extreme exercise,
- knee replacement.

Diet Intervention. All foods will be provided under the direction of study personnel and will be delivered weekly to participants' home address. Weekly contact will maintain retention in the intervention and improve adherence. The Dietary Guidelines for Americans suggests 225-325 g of carbohydrates/day. Therefore, those participants consuming less than 100 g/day would be considered as consuming a reduced-carbohydrate diet and will be excluded. Participants are directed to reduce their total (not net) carbohydrate intake to ≤ 40 g/day. Meals will be offered such that no combination of chosen meals will exceed our limit. Fats will not be restricted, nor will protein (meats, eggs). Fruits will be restricted and vegetables permitted in limited quantities (2 cups/day of leafy greens, 1 cup/day non-starchy vegetables, etc.). Participants will be instructed as to the types and quantities of beverages that are permitted to accompany the LCD. Daily or almost-daily consumption of sugar-sweetened beverages was associated with lowered optimism in chronic pain sufferers and greater risk for depression in healthy women. Artificial carbohydrate-free sweeteners (stevia or sucralose) will be permitted, but powdered sweeteners (aspartame, saccharin, stevia, sucralose) can only be used in limited quantities as they contain maltodextrin (1 g of rapidly digesting carbohydrate). LCDs are known to be safe and first-line treatments for diabetes. LCDs are also known to reduce inflammatory biomarkers to a greater extent than low-fat diets. In fact, a LCD resulted in improved insulin sensitivity as well as reduced triglycerides even when weight loss was accounted for.

Anthropocentric Measures. Body weight, height, waist circumference, blood pressure, and heart rate will be assessed.

Pain-Specific Questionnaires. Pain and disability will be measured using the Brief pain Inventory (BPI) short form and the Western Ontario and McMaster Universities Osteoarthritis Index (WOMAC). The BPI is used to assess the severity of pain and the degree to which that pain interferes with daily activities. This inventory also allows for reports on medications used to treat pain. The WOMAC is commonly used in studies of arthritis and has been validated in numerous clinical trials. Specifically, the WOMAC allows for assessment of pain and interference, but also is specific to aspects of stiffness in the joints not accessed by other surveys. The investigators have previously utilized these measures for chronic pain sufferers. These assessments will be given at baseline and every 3 weeks.

Evoked Pain Testing. Functional tests will be carried out by study personnel. Participants will rate the intensity and unpleasantness of the pain in their affected knee (0-100 scale) prior to and immediately following the tests. The numerical rating scale will be anchored at 0 (no pain) and 100 (worst pain imaginable). Questionnaires will be given between each task to allow for a rest period. Task order will be randomized.

Temporal summation will be assessed on the patellar of the affected knee using a nylon monofilament (Touch test Sensory Evaluator 6.65) calibrated to bend at 300 g of pressure. Participants will provide a pain rating following a single contact of the monofilament, after which they will provide another pain rating following a series of 10 contacts (at a rate of one contact

per second). The change in pain ratings for single versus multiple contacts reflects temporal summation.

Repeated chair stands is a portion of the Short Performance Physical Battery. Participants are asked to stand from a sitting position five times in a row as fast as possible with arms crossed. The time to completion and number of successful stands is scored as the degree of ability.

Timed Up-and-Go is a common task for evaluating pain interference of everyday activities. From a seated position, participants will be asked to get up, walk 10 feet, turn and return to the chair. Time to complete the task will be recorded.

Timed walk will be the final task included. As in the Short Performance Physical Battery, a distance of 15 feet will be marked out on the floor. Participants will complete the distance walking at normal gait speed twice and the time to complete each walk will be recorded.

Quality of Life and Emotional State. Quality of Life will be measured using the short form 36 (SF-36) every 3 weeks. The SF- 36 measures general health status and quality of life across eight domains that are relevant for assessment of a diet intervention. The domains include physical functioning, role limitations due to physical health, bodily pain, general health perceptions, vitality, social functioning, role limitations due to emotional problems, and mental health. The SF-36 has demonstrated reliability and validity in older adult populations and in diet intervention studies. Depression and mood will be assessed using the Patient Health Questionnaire (PHQ-9), which assesses the DSM-IV criteria for depression and can measure depression severity and response to intervention. Participants with PHQ-9 scores >15 will be referred to University of Alabama at Birmingham (UAB) Psychiatry Services for evaluation, as will participants identifying suicidal ideation of any duration on question 9.

Investigating Racial Differences in Diet Benefits for Knee Osteoarthritis

Study Protocol & Statistical Analysis Plan

NCT04343716

08/13/2024

[name], Associate Professor, Principal Investigator University of Alabama at Birmingham Birmingham, AL 35294

Statistical Analysis Plan

For primary outcome measures (WOMAC pain, WOMAC function, BPI pain severity, BPI pain interference, evoked pain tests), a change score will be calculated between baseline measures and those taken at the end of the intervention. To determine whether there are differences based on racial group, an analysis of variance (ANOVA) will be carried out with "race" as the between-subjects factor. Main effects of race will be reported.

Revised Plan

Following recruitment, it was determined that the limited number of non-Hispanic White (NHW) women in the study would make analysis of proposed aims impossible. Therefore, it was decided that the analysis would be altered to determine whether the non-Hispanic Black (NHB) women experienced a change over time in response to the diet intervention across the previous outcome measures. As such, all variables will be analyzed using repeated measures ANOVA and the Greenhouse-Geisser correction will be used when violations of sphericity are detected.

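### Should the Revised Plan still report an estimate of the racial difference once too few NHW women were recruited?

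*SAP*

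**What the plan says.** The title is "Investigating Racial Differences in Diet Benefits for Knee Osteoarthritis", and the Protocol's Participants paragraph plans "20 adult women (55-75) with knee OA with equal representation across racial groups (10 AA, 10 NHW"). In the SAP, the opening paragraph sets the original analysis: "To determine whether there are differences based on racial group, an analysis of variance (ANOVA) will be carried out" on change scores from baseline to the end of the intervention. It adds: "Main effects of race will be reported".

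The Revised Plan replaces this. It states that "the limited number of non-Hispanic White (NHW) women in the study would make analysis of proposed aims impossible", and that "it was decided that the analysis would be altered to determine whether the non-Hispanic Black (NHB) women experienced a change over time" on the same outcomes, analysed by repeated measures ANOVA. It gives no number enrolled or completing for either racial group. It mentions no listing, summary or contrast involving the NHW women. It also mentions no descriptive statistics for the NHB women. I take the Protocol's AA group and the SAP's NHB group to be the same.

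**The concern.** A within-group change in NHB women cannot show whether the benefit differs by race, which is what the title and the original analysis ask. A small comparison group is a good reason to drop a confirmatory test, but it does not by itself make estimation impossible. With two or more NHW completers, a difference in mean change and its confidence interval exist arithmetically.

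The plan speaks of NHW women who were in the study, so some appear to have been enrolled, yet they enter no stated analysis. Without the counts, a reader cannot tell whether the race contrast could not be estimated or was only too imprecise to test. At stake are the reading of an NHB-only result under this title, and whether group means and SDs would be available for a later synthesis.

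**Working it through.** **Inputs.** The Protocol gives the planned 10 v 10 split. The achieved counts are not given. I assume k = 1, 2, 3 or 5 NHW completers and either n = 10 NHB completers or n = 20 − k (the planned total kept). The documents give no SD, effect size, alpha or power, so the planned 20 cannot be reproduced from a calculation. Results are in units of the SD of change; a 5% two-sided level and a 0.8 SD difference are illustrative assumptions.

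**Formulas.**
- Equal-variance 95% half-width = t(0.975, n + k − 2) × √(1/n + 1/k).
- Welch half-width (equal observed SDs) = t(0.975, df) × √(1/n + 1/k), with df = (1/n + 1/k)² / [(1/n)²/(n − 1) + (1/k)²/(k − 1)].
- Power from the noncentral t distribution.

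**Worked cases.**
- Planned 10 v 10: 2.101 × √0.2 = 0.940.
- 10 v 2, pooled: 2.228 × √0.6 = 1.726.
- 10 v 2, Welch: df = 0.36 / (0.01/9 + 0.25) = 1.43, giving 4.975.

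| NHB v NHW | Equal-variance half-width | Welch half-width (df) | Power for 0.8 SD |
|---|---|---|---|
| 10 v 10 (planned) | 0.940 | 0.940 (18) | 39.5% |
| 10 v 5 | 1.183 | 1.260 (8.1) | 27.3% |
| 15 v 5 | 1.085 | 1.225 (6.9) | 31.1% |
| 10 v 3 | 1.449 | 1.987 (3.3) | 19.9% |
| 17 v 3 | 1.316 | 2.096 (2.8) | 22.7% |
| 10 v 2 | 1.726 | 4.975 (1.43) | 15.5% |
| 18 v 2 | 1.566 | 6.126 (1.23) | 17.4% |
| 10 v 1 | 2.373 | none | 10.5% |
| 19 v 1 | 2.156 | none | not run |

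These rows are scenarios, not bounds. With fewer NHB completers the intervals widen: 8 v 2 gives 2.306 × √0.625 = 1.82, and 7 v 3 gives 2.306 × √0.476 = 1.59.

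**Is the narrower interval trustworthy?** The pooled interval borrows nearly all its variance from the NHB group. In simulation (normal data, 200,000 replicates per case, NHW SD twice the NHB SD) its nominal 95% coverage was:
- 88.2% at 10 v 5 and 84.2% at 15 v 5
- 82.7% at 10 v 3 and 78.0% at 17 v 3
- 78.7% at 10 v 2 and 74.3% at 18 v 2

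With two or three NHW women there is almost no information with which to check that assumption. The Welch interval avoids it only by becoming 2 to 6 SD either side.

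**Volume.** The primary outcomes are four questionnaire scales plus the evoked pain tests. The Protocol describes four such tests (temporal summation, chair stands, Timed Up-and-Go, timed walk). Counting one measure per test, that is 4 + 4 = 8 outcomes, and two intervals each makes 16.

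**Disclosure.** For two women the SD is the absolute difference divided by √2, so the two values are mean ± SD/√2. A published mean and SD for two women is therefore a listing of individual data, at a single site with race, sex and age band known.

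**Pooling everyone instead.** Adding k NHW women to 10 NHB women lowers the standard error of the overall mean change by 1 − √(10/(10 + k)): 8.7%, 12.3% and 18.4% at k = 2, 3 and 5. With a total of 20 the reduction, 1 − √((20 − k)/20), is 5.1%, 7.8% and 13.4%. This is a modest gain for a population mix set by recruitment, and it does not address race.

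**The case for a change.** The strongest case for a change is that low precision does not separate the plan that was adopted from the one that was abandoned. The planned 10 v 10 comparison itself had about 40% power for 0.8 SD. With 10 NHB and 5 NHW women the interval would be only 1.183/0.940 = 1.26 times as wide. If the NHW count was near 5, calling the aim impossible overstates the difficulty. Counts and a scope statement cost almost nothing whatever the number, and participants who completed a 6-week diet arguably deserve to appear in the results.

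Part of this stands. The word is too strong unless the NHW count was zero or one, and the counts should be visible to readers. Two things limit it. First, the plan says the proposed aims cannot be analysed; it does not say that the NHW data will go undescribed. A two-paragraph SAP that names no descriptive statistics for anyone is brief, and its silence is not a decision to exclude. The documents do not show what was finally reported. Second, the case for an interval is respectable only towards k = 5, and nothing in the documents says that k was that large.

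**Conclusion.** No change to the plan is needed. Dropping the race test was reasonable on any of the assumed counts: power for 0.8 SD would be 27 to 31% at 5 NHW women and 16 to 23% at 2 to 3. The plan attributes the change to recruitment, restates its question as NHB change over time and does not claim that this answers the race question, so carrying it out as written gives no wrong result here.

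The one substantive addition, an interval for the racial difference, is optional. At 2 to 3 NHW women it is close to uninformative (1.32 to 1.73 SD if variances are assumed equal, 1.99 to 6.13 SD if not), and at two it raises a disclosure problem. A statistician could reasonably decline it. Counts by race, a note that the NHB result does not speak to racial differences, and NHW summaries where disclosure allows are ordinary content of a results report.

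This rests on an NHW count that the documents do not give, on at least 10 NHB completers for the quoted ranges, and on an illustrative 0.8 SD difference.

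### The Revised Plan attributes change over visits to the diet, which a one-group, uncontrolled repeated measures ANOVA chosen after recruitment cannot show

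*SAP*

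**What the plan says.** The SAP first planned that, for each primary outcome, "a change score will be calculated between baseline measures and those taken at the end of the intervention", with those scores compared between racial groups by ANOVA.

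The Revised Plan replaces this and explains why: "Following recruitment, it was determined that the limited number of non-Hispanic White (NHW) women in the study" ruled out the planned aims. The new purpose is to "determine whether the non-Hispanic Black (NHB) women experienced a change over time in response to the diet intervention across the previous outcome measures". On method, "all variables will be analyzed using repeated measures ANOVA and the Greenhouse-Geisser correction will be used when violations of sphericity are detected". No between-subjects factor remains.

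The protocol describes a single intervention. Under Diet Intervention, "Participants are directed to reduce their total (not net) carbohydrate intake" to a fixed daily limit, with no alternative diet, waiting-list group or allocation to diet. The only randomisation anywhere is of the order of the functional tasks (Evoked Pain Testing). The opening paragraph says that "participants will be asked to select one week of meals and snacks from a menu of commercially-available meals", and that "Every three weeks, participants will return for testing". For the pain questionnaires, "These assessments will be given at baseline and every 3 weeks". This gives three time points: baseline, week 3 and week 6.

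**The concern.** The revised question has two parts: whether scores changed, and whether the diet was the reason. The planned test addresses only the first. Once the race comparison is gone, the second is the only inferential claim the trial makes, and nothing in the design or analysis supports it.

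The documents contain several other routes to improvement over six weeks:

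- Women enter because they have had pain on most days for three months, so some regression to the mean is possible. There is no severity cut-off, so its size is unknown.
- Participants choose their study meals, know what they are eating and rate their own pain, so expectation can act.
- Study staff contact them every week.
- Knee pain may vary naturally over six weeks.
- Practice may help on the timed tasks. The change score in the initial analysis implies that these are done at least twice.

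The pain and functional outcomes are all tested under the same sentence. Any that reaches significance could be reported, in the plan's own terms, as a response to the diet.

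**Working it through.** **What the ANOVA tests.** With one group and visit as the only factor, the null hypothesis is that mean scores are equal at baseline, week 3 and week 6. Write the mean change at a visit as diet effect plus non-diet drift. The data identify only the sum. Splitting it needs a concurrent comparison or an outside estimate of drift, and the plan has neither. The week of food and pain recording before the diet is not used in the SAP as a control period.

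**Why the initial plan differed.** It had no diet control either, but it compared change between racial groups, so drift shared equally by both groups would cancel. In a one-group time effect nothing cancels.

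**Illustration of size.** The plan states no power, SD or alpha, so there is no figure to reproduce. Assumed inputs:

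- n = 10, the number of African American women planned in the protocol; the achieved NHB count is not given
- three visits, alpha 0.05, compound symmetry
- SD of the change score = 1, so residual variance is 0.5
- true diet effect zero, non-diet drift d by week 6

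The noncentrality is n × (sum of squared deviations of the visit means) / 0.5, referred to F(2, 18).

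- Linear drift (means 0, d/2, d): the sum of squares is d²/2, so λ = n·d². For d = 0.3, λ = 10 × 0.09 = 0.90. For d = 0.5, λ = 10 × 0.25 = 2.50.
- Drift complete by week 3 (means 0, d, d): the sum of squares is 2d²/3, so λ = (4/3)·n·d². For d = 0.3, λ = 1.20. For d = 0.5, λ = 3.33.

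Probability of a significant time effect, per outcome:

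| Drift pattern | Correction | d = 0.3 | d = 0.5 |
|---|---|---|---|
| Linear | none | 0.112 | 0.237 |
| Linear | Greenhouse-Geisser always | 0.094 | 0.207 |
| Complete by week 3 | none | 0.134 | 0.305 |
| Complete by week 3 | Greenhouse-Geisser always | 0.113 | 0.267 |

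The Greenhouse-Geisser rows come from simulation (200,000 runs). The ranges are therefore about 9–13% and 21–30%.

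**Sensitivity to scaling.** If drift is expressed in baseline SDs, the SD of the change score is √(2(1 − ρ)). At ρ = 0.5 this is 1, and at ρ = 0.7 it is √0.6 = 0.77. With drift complete by week 3, simulation (20,000 runs) gives 13–20% for 0.3 SD and 30–48% for 0.5 SD at n = 10, and 25–39% and 60–83% at n = 20. With no drift the rate is about 5%. A two-arm comparison in which both arms share the drift also stays near 5% (0.048–0.052).

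**Plausibility of such drift.** Regression to the mean alone gives an expected shift of (1 − ρ) × baseline excess. For ρ of 0.5 to 0.7 and an assumed excess of 0.5 to 1.0 SD, this runs from 0.3 × 0.5 = 0.15 to 0.5 × 1.0 = 0.50 baseline SD.

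**Precision.** At n = 10 the 95% confidence interval for a mean change has half-width t(0.975, 9)/√10 = 2.262/3.162 = 0.715 SD of the change score.

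**The case against.** The strongest reply is that this is a matter of wording. Repeated measures ANOVA is a valid test of change over time, no model or p-value would alter, and in a single-arm study the phrase might simply mean change during the diet period. The switch, its timing and its reason are disclosed, and a reader can see that there is no control group. The initial design had no diet control either.

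Much of this stands. The test is sound for the question whether scores changed, the disclosure deserves credit, and the revision did not remove a diet control. The loose reading is less convincing: the sentence already says the change is over time, so the added reference to the diet can only supply a cause. Disclosing why the plan changed does not tell the reader how to interpret a significant time effect.

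Two further points limit the argument. Entry rests on a three-month pain history screened by telephone, and baseline measures come later, so selection is not on the baseline score itself. That should weaken regression to the mean without removing it. The percentages depend on assumed drift and on its scaling, and they are power to detect real drift, not type I error. They show the mechanism and do not estimate bias in this trial.

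**Conclusion.** The concern holds. The stated objective claims more than the design can deliver: the data can support a statement that scores in NHB women changed over the six weeks, but not that the diet changed them. This follows from the absence of any comparator and does not depend on the illustration.

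Under the assumptions of 10 women, no diet effect, and drift of 0.3 or 0.5 SD of the change score, a significant result that could be credited to the diet would arise about 11% or 24% of the time per outcome. With more women, or with drift of that size in baseline SDs and higher within-person correlation, the rates would be higher. The true drift and the achieved sample size are unknown. The point should be fixed before results are reported, but it does not prevent the analysis from going ahead.

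**What to change.** In the Revised Plan, delete the words that attribute the change to the diet and replace the sentence stating the new purpose with:

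> The analysis will estimate the mean change from baseline over the 6-week intervention in NHB women, with 95% confidence intervals reported alongside the repeated measures ANOVA. This analysis was defined after recruitment, is uncontrolled and is hypothesis-generating; it supports no claim that the diet caused the change.

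The second sentence corrects the attribution. The confidence intervals do not, but they show how little precision a group of this size offers.

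The planned test and its sphericity correction stay as they are. The cost is two sentences of SAP text and intervals computed from data already in the analysis. The downside is a weaker claim, which is the one the design supports.
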